### 5.3 Exclusion Criteria

Patients with RCLAD will be excluded if they are, in the judgment of the investigator, unlikely to tolerate pirfenidone. Other exclusion criteria will include:

1. FVC decline related to non-RCLAD causes (e.g. pulmonary edema, pleural effusion, etc).
2. Patients with any severe comorbidity complicating RCLAD which might determine their prognosis and functional level (e.g. active malignant disease) within the last 12 months.
3. Patients who have resumed smoking after transplantation.
4. Renal insufficiency (creatinine clearance < 30 ml/min calculated by the CKD-Epi formula).
5. Total bilirubin above the upper limit of the normal range (ULN)
6. Aspartate or alanine aminotransferase (AST or ALT) > 3 times the ULN.
7. Known allergy of hypersensitivity to Pirfenidone
8. Ongoing use or expected use of any of the following therapies:
  - Strong inhibitors of CYP1A2 (e.g. fluvoxamine or enoxacin).
  - Moderate inhibitors of CYP1A2 (e. g. mexiletine, thiabendazole, or phenylpropanolamine). Ciprofloxacin will be allowed only at doses equal or less than 500 mg BID.
9. Inability to provide informed consent.

## 6 STUDY PROCEDURES AND GUIDELINES

A Schedule of Events representing the required testing procedures to be performed for the duration of the study is diagrammed below.

| Week                   | 1 | 2 | 3 | 4 | 5 | 6 | 8 | 12 | 16 | 20 | 24 | 28 | 32 | 36 | 40 | 44 | 48 | 52 | 56 | 57 | 60 |
|------------------------|---|---|---|---|---|---|---|----|----|----|----|----|----|----|----|----|----|----|----|----|----|
| Start Pirfenidone      | x |   |   |   |   |   |   |    |    |    |    |    |    |    |    |    |    |    |    |    |    |
| Study coordinator call |   | x |   | x |   | x |   | x  | x  | x  | x  | x  | x  | x  | x  | x  | x  | x  | x  | x  |    |
| Tacrolimus level       | x | x | x | x | x | x | x | x  | x  | x  | x  | x  | x  | x  | x  | x  | x  | x  | x  | x  | x  |
| Liver function tests   |   |   |   | x |   |   | x | x  | x  | x  | x  |    |    | x  |    |    | x  |    |    |    |    |
| Clinic visit           |   |   |   |   |   |   | x |    |    | x  |    |    | x  |    |    | x  |    | x  |    |    |    |
| FVC measure            |   |   |   |   |   |   | x |    |    | x  |    |    | x  |    |    | x  |    | x  |    |    |    |
| CT scan                |   |   |   |   |   |   |   |    |    |    | x  |    |    |    |    |    |    |    |    |    |    |
| Stop Pirfenidone       |   |   |   |   |   |   |   |    |    |    |    |    |    |    |    |    |    |    |    | x  |    |

Prior to conducting any study-related activities, written informed consent must be signed and dated by the subject.

Any clinically significant findings will be communicated to the patients and, with their consent, to the patients' clinical providers.

**Study coordinator call:** Our study coordinator will contact subjects by phone every 2 weeks for the first 6 weeks to inquire about treatment-emergent adverse events (TEAE) and then monthly. TEAE will be recorded and graded according to the Common Terminology Criteria for Adverse Events (CTCAE) v3.0^21. The last phone call will be 28 days after the last pirfenidone dose. Subjects will be provided a phone number to report any additional TEAE. A Data Safety Monitoring Board will be convened.

**Tacrolimus concentration measurement:** Patients will continue to use their chosen laboratory for tacrolimus measurement, as part of their clinical care. As it is our clinical practice, the results will be reviewed daily through Titus and the transplant nurse coordinators will contact the patients with instructions to adjust their tacrolimus dose.

**Liver function test measurement:** Patients will continue to use their chosen laboratory for monthly liver function test measurement according to the post-transplant surveillance protocol. We will track these values every month for the first 6 months of Pirfenidone therapy and every 3 months for the remaining 6 months, following manufacturer's recommendations.

**Office spirometry (FVC):** As part of their clinical care, patients will have office FVC measurement (spirometry) approximately every 3 months or more often if clinically indicated according to ATS/ERS guidelines.

**High-resolution chest CT (HRCT):** Patients will have a HRCT every 6 to 12 months as part of their clinical care. We will review these images to evaluate fibrosis scores.

**Reporting of clinical events:** All patients will be asked to report clinical events (e.g. new or worsening symptoms, unscheduled medical visits, hospitalizations) to the study coordinator over the phone. The study coordinator will ask the transplant nurse coordinators and review the medical record to investigate if any other events occurred.

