## PROTOCOL SYNOPSIS

|                                   |  |
|-----------------------------------|--|
| TITLE                      | PIRFENIDONE FOR RESTRICTIVE ALLOGRAFT DYSFUNCTION (PIRCLAD)   |
| SPONSOR                    | Nina Ireland Program for Lung Health discretionary funds from [name]   |
| FUNDING ORGANIZATION       | UCSF   |
| NUMBER OF SITES            | 1  |
| RATIONALE                  | 
Long-term survival after lung transplant is limited by the development of chronic lung allograft dysfunction. In approximately 30% of cases, chronic lung allograft dysfunction has a restrictive phenotype (RCLAD) characterized by fibrosis with rapid progression. Approximately 60% of patients with RCLAD die within one year from respiratory failure. Currently, there are no therapies available for RCLAD. Due to the similarities between RCLAD and Idiopathic Pulmonary Fibrosis (IPF), there is keen interest in the transplant community to investigate the effect of the anti-fibrotic drug pirfenidone in RCLAD. Pirfenidone has been proved to slow the progression of IPF and is approved by the Food and Drug Administration (FDA) for that indication.
 
This protocol will evaluate the safety and tolerability of pirfenidone in lung transplant recipients with RCLAD. The results of this pilot study will provide the foundation for a multicenter randomized control trial to evaluate the efficacy of pirfenidone in slowing the progression of RCLAD.
 |
| STUDY DESIGN               | Interventional, open-label, pilot study  |
| PRIMARY OBJECTIVE          | Asses the safety and tolerability of Pirfenidone in lung transplant recipients with RCLAD.   |
| NUMBER OF SUBJECTS         | 10   |
| SUBJECT SELECTION CRITERIA | 
Inclusion Criteria:
 
Subjects aged 18 to 80 years old, who underwent bilateral lung transplantation at UCSF and have a diagnosis of RCLAD based on the International Heart and Lung Transplant (ISHLT) classification.
 
The diagnosis of RCLAD is based on spirometry (FEV1 <math>\leq</math> 80% and FVC <math>\leq</math> 80% of best post-transplant baseline) and CT scan (e.g. pleuroparenchymal fibroelastosis) findings.
 
Subjects with steady-state blood concentration of tacrolimus, as
   |

|  |   |
|--|---|

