| SAFETY EVALUATIONS
(PRIMARY OUTCOMES)               | 
Tolerability of pirfenidone: The primary outcome will be the number of subjects that discontinue pirfenidone due to a treatment emergent adverse event (TEAE). A secondary outcome will be the proportion of subjects experiencing a TEAE.
 
Tacrolimus dose change: The outcome will be the ratio of tacrolimus-on-pirfenidone to tacrolimus-off-pirfenidone corrected for the subject's specific steady-state tacrolimus concentration. Subjects with steady-state blood concentration of tacrolimus, as assessed by 10-12 hour trough level, will initiate pirfenidone. Tacrolimus trough level will be measured weekly for the first 6 weeks after starting pirfenidone. Another measurement will be done at week 8. Once a therapeutic blood concentration (8-12 ng/ml) is achieved, measurements will be done monthly. First, we will calculate the concentration-to-dose ratio of tacrolimus on and off pirfenidone by dividing the tacrolimus blood concentration by the corresponding total daily dose of tacrolimus for each period. To obtain the conversion ratio, then we will divide the concentration-to-dose ratio for tacrolimus-on-pirfenidone by the concentration-to-dose ratio for tacrolimus-off-pirfenidone ([blood concentration on pirfenidone/daily dose on pirfenidone]/[blood concentration off pirfenidone/daily dose off pirfenidone]).
 |
| EFFICACY EVALUATIONS                                    | 
FVC decline: We will evaluate change in FVC every 3 months after initiation of pirfenidone.
   |

|   |   |
|---|---|
| (SECONDARY OUTCOMES)             | 
Radiographic progression: We will evaluate fibrosis scores on chest CT at RCLAD onset and in the follow up CT scans performed as part of routine clinical care.
   |
| PLANNED INTERIM ANALYSES         | Quarterly   |
|   |   |

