## 4 STUDY DESIGN

### 4.1 Study Overview

1) We will screen for eligible subjects using the computer algorithm on spirometry data abstracted from Apex monthly and by suggestion of the transplant pulmonologists. 2) Then, we will review CT scans to adjudicate a diagnosis of RCLAD. 3) Finally, our pharmacist will determine if tacrolimus dose is stable. After these 3 steps are completed subjects will be eligible for the study.

Subjects will be recruited at their transplant clinic visit or by phone if they previously consented to be contacted with new research study opportunities. We will seek to enroll ten subjects, who will receive pirfenidone for 52 weeks, titrated to 2403 mg/day (3 capsules, 3× daily) over a period of six weeks. Genentech has agreed to provide study drug free of cost.

TEAE will be recorded and graded according to the Common Terminology Criteria for Adverse Events (CTCAE) v3.0^21. Our study coordinator will contact subjects by phone every 2 weeks for the first 6 weeks to inquire about TEAE and then monthly. Subjects will be provided a phone number to report any additional TEAE. A Data Safety Monitoring Board will be convened.

As part of their routine post-transplant surveillance, subjects have monthly laboratory testing that includes tacrolimus blood concentration and liver function tests. Therefore, the manufacturer recommendations of monitoring liver function tests monthly for the first six months and then every 3 months while taking Pirfenidone, will be followed.

Subjects will continue their routine care with clinic visits, spirometry and CT as clinically indicated. In our clinical practice, subjects with RCLAD are expected to have a clinic visit and spirometry approximately every 3 months and a CT scan every 6 to 12 months.

If RCLAD subjects in the study undergo bronchoscopy for a clinical indication, bronchoalveolar lavage, biopsies, airway brushes and plasma specimens will be collected in the biorepository for future analysis of changes in pro-fibrotic mediators after initiation of pirfenidone. These specimens will be collected as part of the ongoing "Lung Transplantation: Improving outcomes through the development of a clinical database and biorepository" study number 13-10738. In the future, we plan to explore whether subjects with RCLAD have a greater rate of decline in telomere length in airway epithelial cells compared subjects without RCLAD.

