### 5.2 Inclusion Criteria

1. Subjects aged 18 to 80 years old who underwent bilateral lung transplantation at UCSF.
2. Diagnosis of RCLAD based on the International Heart and Lung Transplant (ISHLT) classification. The diagnosis of RCLAD is based on spirometry (FEV1 ≤ 80% and FVC ≤ 80% of best post-transplant baseline) and CT scan (e.g. pleuroparenchymal fibroelastosis) findings.
3. Subjects with steady-state blood concentration of tacrolimus, as assessed by 10-12 hour trough level.

[figure not shown]

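### CT fibrosis is scored by the unmasked study team, and with no pre-dose CT secured the radiographic change may include an unknown amount of untreated progression

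*Combined protocol and SAP*

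**What the plan says.** The Synopsis describes the study as "Interventional, open-label, pilot study" and lists no control product. Its radiographic outcome reads: "We will evaluate fibrosis scores on chest CT at RCLAD onset and in the follow up CT scans performed as part of routine clinical care". Section 3.2 makes slower radiographic progression part of the secondary objective, and Section 2 wants early evidence of it for the design of a randomised trial.

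On who reads the scans, Section 4.1 has as its second screening step: "Then, we will review CT scans to adjudicate a diagnosis of RCLAD". Under Section 5.2 the diagnosis rests on spirometry "and CT scan (e.g. pleuroparenchymal fibroelastosis) findings". For the outcome, Section 6 says: "We will review these images to evaluate fibrosis scores". The Data and Safety Monitoring Plan (Data Review) has the investigators discuss each patient's treatment and responses at monthly meetings. The document names no scoring system, no masked or independent reader, and no masking of scan date or order.

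On timing, Section 6 says: "Patients will have a HRCT every 6 to 12 months as part of their clinical care". The only CT mark in the main Schedule of Events is in the week 24 column; none stands at or before week 1. Sections 5.2 and 5.3 set no limit on time from RCLAD onset to enrolment. Section 8 assigns fibrosis score to mixed effects models, with subject as a fixed effect, and plans to compare slopes before and after pirfenidone starts.

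**The concern.** Two separate features weaken the radiographic result.

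**Reading.** A fibrosis score involves judgement. Here it is made by a team that knows every subject is on the drug and follows each subject's course month by month. As far as the plan says, readers may also see which scan came first. Any systematic shift between earlier and later reads passes one-for-one into each subject's change. In a controlled trial with masked reading, such a shift would largely cancel between arms. Here nothing cancels it.

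**Timing.** The only pre-treatment scan that the plan names is the one at RCLAD onset. If months pass between onset and first dose, change measured from that scan includes progression that pirfenidone had no chance to affect.

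At stake is the use that Section 2 makes of this outcome. If drug effect, reader expectation and untreated progression cannot be told apart, the radiographic data offer little guidance for the next trial.

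**Working it through.** The plan states no figure for the radiographic outcome, so there is none to reproduce. Two checks apply.

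**1. Untreated share of the onset-to-CT interval.**

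Inputs:
- g = weeks from the onset CT to first dose. It is not given; assumed range 0 to 52.
- t = weeks from first dose to the follow-up CT. It is 24 from the Schedule of Events; 52 is taken as an upper case, because Section 6 allows up to 12 months between scans.
- Progression is assumed linear.

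Untreated share = g/(g + t).

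| g (weeks) | CT at week 24 | CT at week 52 |
|---|---|---|
| 0 | 0% | 0% |
| 4 | 4/28 = 14% | 4/56 = 7% |
| 13 | 13/37 = 35% | 13/65 = 20% |
| 26 | 26/50 = 52% | 26/78 = 33% |
| 52 | 52/76 = 68% | 52/104 = 50% |

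To show the consequence, suppose the drug truly halves the slope (an assumption, for illustration only). The onset-to-CT slope would then show a reduction of 0.5 × t/(g + t). With a week-24 CT that is 50% at no lag, 0.5 × 24/37 = 32% at 13 weeks and 0.5 × 24/76 = 16% at 52 weeks. On this reading, untreated time dilutes a real effect.

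**2. Can the before/after slope comparison in Section 8 separate the two periods?**

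Each subject needs three parameters: a level, a pre-drug slope and a post-drug slope, with the bend at first dose.

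- One subject with an onset scan and one week-24 scan gives 2 scores for 3 parameters (rank 2 of 3). No within-subject contrast exists.
- Ten such subjects with the same lag give 20 scores for 10 levels plus 2 common slopes. The design has rank 11 of 12, so the contrast is still not estimable.
- Ten such subjects with varying lags reach rank 12 of 12, but only by assuming that all subjects share the same two slopes. Under two assumed lag patterns (4 to 40 weeks in steps of 4; 4 to 49 weeks in steps of 5), the standard error of the slope difference is 0.077 and 0.068 residual SD per week. With a scan at treatment start as well, it would be 0.030 and 0.027. The ratio is about 2.5.
- One subject with a third scan, either before first dose or later in follow-up, reaches rank 3 of 3. The contrast exists, with no residual degrees of freedom within that subject.

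So the Section 8 comparison works only for subjects who happen to have more scans than the plan names, or by borrowing across subjects under a common-slope assumption.

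**Reader shift.** The documents give no score, scale or variability, so no size can be computed.

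**The case against.** The strongest reply is Section 8. The plan does not define the outcome as change from onset, and it never calls the onset CT a baseline. In a slope comparison, the onset scan anchors the pre-drug slope. Routine CTs every 6 to 12 months may also give some subjects the extra scans they need. This stands in part: the plan intends the right contrast. What it does not do is require or name the scans that would make the contrast estimable, and slope modelling does nothing about unmasked reading.

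Several stronger readings are tempting, and the documents do not carry them:

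- A reader might infer that the scan used for entry and the onset scan are the same image. No sentence says so.
- A reader might infer a two-way incentive, with high scores at entry and stable scores later. Adjudication at entry is a diagnosis, not a score. Nothing says that onset scores are assigned at screening, that scans are scored as they arrive, or that one individual does both. What the text supports is that reader, scoring system and masking are unspecified in a team that knows the treatment.
- A reader might take the lag to be long. Spirometry is screened monthly, which could keep it short for new cases, but nothing bounds it.

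It is also fair to say that this is a secondary outcome in a 10-subject pilot that seeks only early evidence.

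**Conclusion.** The concern holds in two parts. First, the radiographic outcome is open to reader expectation, because scoring rests with an unmasked team in a study with no control arm; the size is unknown. Second, an onset-to-follow-up change would contain untreated progression, and the planned slope comparison cannot remove it within a subject who has only an onset scan and one follow-up scan.

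The percentages above rest on linear progression and on assumed lags. If subjects start soon after onset, the second part has little effect. The net direction is not fixed: untreated time would dilute a real effect, while reader expectation could favour the drug. It would go too far to conclude that the plan will report untreated progression as drug effect, or that bias has been shown. Tolerability and tacrolimus, the primary outcomes, are not touched.

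**What to change.** 1. **Masked batch scoring** (Synopsis, radiographic outcome; Section 6, HRCT). State that after the last main-phase CT the same reader will re-score every scan, including all available pre-dose scans, in one batch with dates and identifiers removed and order randomised. Only these scores enter the outcome. Repeat the batch for the extension. This fits the separate main-phase and extension publications in Section 10.4. Name the scoring system.

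2. **Time from first dose** (Synopsis; Section 8, or the SAP that Section 8 promises). Model scores by scan date relative to first dose. Use all available pre-dose CTs for the pre-drug slope and the last pre-dose CT as the on-drug reference. Report each subject's interval from that CT to first dose. Where the onset scan is the only pre-dose CT, describe the result as onset-to-follow-up change, not on-drug change.

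The second change cannot recover information for a subject with no later pre-dose scan; there it only prevents a wrong label. The cost is wording and the de-identification of a few existing scans per subject, with no new scan or reader. The drawbacks are that final scores come only at the end of follow-up and that the reader may recognise some cases.

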#### Protocol Amendment

Subjects that wish to continue taking pirfenidone beyond 56 weeks may be eligible for PIRCLAD extension for up to 76 weeks. The Principal Investigator will determine eligibility for PIRCLAD extension after reviewing the 52-week study coordinator call. Subjects must continue to meet the original inclusion and exclusion criteria. Subjects will continue to be monitored per study protocol (laboratory tests, study coordinator calls, clinic visits, pulmonary function tests, and CT scan imaging) as long as they remain on pirfenidone. The last pirfenidone dose will be on September 30, 2021. The last study coordinator call will occur 28 days after the last pirfenidone dose. Reporting of adverse events and protocol violations for these subjects will remain the same. The duration of PIRCLAD extension is diagrammed below.

| Week                   | 56 | 60 | 64 | 68 | 72 | 76 | 80 | 84 | 88 | 92 | 96 | 100 | 104 | 108 | 112 | 116 | 120 | 124 | 128 | 129 | 132 |
|------------------------|----|----|----|----|----|----|----|----|----|----|----|-----|-----|-----|-----|-----|-----|-----|-----|-----|-----|
| Continue Pirfenidone   | x  |    |    |    |    |    |    |    |    |    |    |     |     |     |     |     |     |     |     |     |     |
| Study coordinator call | x  | x  | x  | x  | x  | x  | x  | x  | x  | x  | x  | x   | x   | x   | x   | x   | x   | x   | x   | x   | x   |
| Tacrolimus level       | x  | x  | x  | x  | x  | x  | x  | x  | x  | x  | x  | x   | x   | x   | x   | x   | x   | x   | x   | x   | x   |
| Liver function tests   | x  |    |    | x  |    |    | x  |    |    | x  |    |     | x   |     |     | x   |     | x   |     | x   |     |
| Clinic visit           | x  |    |    | x  |    |    | x  |    |    | x  |    |     | x   |     |     | x   |     | x   |     | x   |     |
| FVC measure            | x  |    |    | x  |    |    | x  |    |    | x  |    |     | x   |     |     | x   |     | x   |     | x   |     |
| CT scan                |    |    |    |    |    |    |    |    |    |    |    |     | x   |     |     |     |     |     |     |     |     |
| Stop Pirfenidone       |    |    |    |    |    |    |    |    |    |    |    |     |     |     |     |     |     |     |     | x   |     |

## 7 PROTOCOL VIOLATIONS

A protocol violation occurs when the subject or investigator fails to adhere to significant protocol requirements affecting the inclusion, exclusion, subject safety and primary endpoint criteria. Failure to comply with Good Clinical Practice (GCP) guidelines will also result in a protocol violation. The investigator will determine if a protocol violation will result in withdrawal of a subject.

When a protocol violation occurs, it will be discussed with the investigator and a Protocol Violation Form detailing the violation will be generated. This form will be signed by the Investigator. A copy of the form will be filed.

## 8 STATISTICAL METHODS AND CONSIDERATIONS

Prior to the analysis of the final study data, a detailed Statistical Analysis Plan (SAP) will be written describing all analyses that will be performed. The SAP will contain any modifications to the analysis plan described below.

**Interim analysis plans:** We will plan interim analyses of data quality and patient compliance on a quarterly basis to insure adequate study conduct. Modifications to the study conduct (e.g. changes to the outcome measures, or even cessation of the study if indicated by issues with performance or outcomes) will be considered at each of these analyses.

**Power:** This is a pilot study with the primary outcome of determining pirfenidone tolerability and its effect on tacrolimus dosing. Even with a small cohort, we hypothesize we will be powered to detect a significance difference in tacrolimus dosing. Based on the single report of tacrolimus dosing increase of 2.5 fold, and conservatively estimating a standardized effect size of 1 (doubling of tacrolimus dose and a standard deviation of the

change of 50%), a sample of 8 subjects would be required to detect a significant difference, assuming a two-sided  $\alpha$  of 0.05 and  $\beta$  of 0.20.

**Data analysis plan:** Since we will be comparing within subject changes, we will use paired t-test to compare the tacrolimus-on-pirfenidone to tacrolimus-off-pirfenidone ratio. For analyses involving repeated measures including change in FVC, fibrosis score, and telomere length, we will use mixed effects models including subject as a fixed effect. Slopes before and after the initiation of pirfenidone will be compared.

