## 2 STUDY RATIONALE

This proposal aims to gather the preliminary data needed to design a multicenter randomized controlled trial (RCT) of pirfenidone for RCLAD. To do so, we first need evidence of tolerability, to understand drug interactions with the immunosuppressive regimen used to maintain allograft function and early evidence that pirfenidone may slow FVC decline and radiographic progression in RCLAD.

Evidence that pirfenidone is well tolerated in transplant recipients and that it slows the progression of RCLAD would be paradigm shifting. Further, identifying subjects at risk for RCLAD before the onset of spirometric changes would allow to start therapeutic interventions sooner, maximizing their benefit. Finding biomarkers that predict response to pirfenidone would identify patients most likely to benefit.

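### The before/after FVC slope comparison names no subject-specific slope and no pre-drug period, so its error rate and its estimate can be wrong in either direction (minor)

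*Combined protocol and SAP*

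**What the plan says.** - **Model.** The data analysis plan in section 8 covers FVC, fibrosis score and telomere length with mixed effects models "including subject as a fixed effect. Slopes before and after the initiation of pirfenidone will be compared". It names no random intercept, random slope or residual covariance. It gives no alpha or test for this comparison; the two-sided 0.05 in that section belongs to the tacrolimus calculation.
- **Outcome.** The synopsis (Efficacy Evaluations) describes FVC change at three-month intervals from drug start onward and mentions no earlier period.
- **Schedule.** Section 6 says "A Schedule of Events representing the required testing procedures to be performed for the duration of the study is diagrammed below". Its first column is week 1, when pirfenidone starts. FVC is marked at weeks 8, 20, 32, 44 and 52, and there is no pre-drug column.
- **Source of readings.** Spirometry is routine care: "patients will have office FVC measurement (spirometry) approximately every 3 months or more often if clinically indicated". Section 4.1 mentions record spirometry only for finding cases: "We will screen for eligible subjects using the computer algorithm on spirometry data abstracted from Apex monthly". No look-back length is given.
- **Contrast with CT.** The synopsis does give CT a starting point: "We will evaluate fibrosis scores on chest CT at RCLAD onset". FVC has none.
- **Later document.** Section 8 promises a detailed SAP before the final analysis, which may modify the plan.

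**The concern.** One of the two slopes to be compared has no defined data, and the only stated subject term lets subjects differ in level but not in rate of decline. Three things can then go wrong.

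1. **Standard error.** With identical visit times, differences in slope between subjects cancel out of the before/after contrast but stay in the residual, so the test is too cautious. With unequal visit times they no longer cancel, and the test rejects too often.
2. **Deaths.** If faster decliners die sooner, the pooled on-drug slope leans towards slower decliners and the drug appears to slow decline.
3. **Window.** Readings taken before decline began flatten the pre-drug slope, and the drug appears to speed decline. A subject-specific slope does not cure this.

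At stake is the secondary objective in section 3.2 and what section 2 wants before a multicentre trial: "early evidence that pirfenidone may slow FVC decline and radiographic progression in RCLAD". The primary outcomes are untouched.

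**Working it through.** The plan gives no FVC sample size, variance or power, so there is no stated figure to reproduce. The 8 subjects in section 8 concern tacrolimus only.

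**Inputs from the documents.** 10 subjects; on-drug FVC at weeks 8, 20, 32, 44 and 52; readings about every 3 months (13 weeks used before drug); 60% one-year mortality as the background figure in the synopsis.

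**Assumed, from no document.** Mean decline 0.5 L/year; between-subject slope SD 0.2 to 0.4 L/year; SD of slope change 0 or equal to the slope SD; residual SD 0.15 L; log-hazard of death 0.3 to 0.8 per SD of faster decline; two-sided 5% test.

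**Models.** With t = 0 at drug start:
- Literal: FVC_ij = a_i + b·t_ij + c·max(t_ij, 0) + e_ij, testing c = 0. Positive c means slowing.
- Per subject: d_i = on-drug slope minus pre-drug slope, each fitted within the subject; t = mean(d) / (SD(d)/√n).

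**Step 1: simulation with no drug effect and linear decline.**

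| Setting | Literal: mean error (L/year) | Literal: rejection | Per-subject: rejection |
|---|---|---|---|
| Common slopes, independent errors | 0 | 4% to 6% | 4% to 6% |
| Slopes differ, equal 9-month window, no deaths | 0 | 0.2% to 2.7% | 4% to 6% |
| Slopes differ, 1 to 5 pre-drug FVCs, no deaths | 0 | 9% to 14% | 4% to 5% |
| Equal 9-month window, 60% mortality | +0.06 to +0.27 | 7% to 30% | 4% to 6% |

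At 30% mortality the false slowing is about 0.03 to 0.15 L/year, and it is smaller at 15%.

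Equal windows do not guarantee caution. With residual SD 0.10 L and only the slope change varying (SD 0.3), the literal test rejected 3.8%, 11% and 29% of null trials for windows of 0.5, 1 and 2 years. Serial correlation of 0.5 to 0.7 per quarter with common slopes gave 16% to 18%.

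**Step 2: the window, by hand.** Take readings at 12, 9, 6, 3 and 0 months before drug, FVC flat until onset, then −0.5 L/year before and after drug. Deviations of t from its mean are −0.5, −0.25, 0, 0.25, 0.5, so Sxx = 0.625.
- Onset 3 months before drug: FVC changes 0, 0, 0, 0, −0.125. Sxy = 0.5(−0.125) = −0.0625; slope = −0.10; apparent change = −0.50 + 0.10 = −0.40.
- Onset 6 months before: 0, 0, 0, −0.125, −0.25. Sxy = 0.25(−0.125) + 0.5(−0.25) = −0.156; slope = −0.25; apparent change = −0.25.
- Onset 9 months before: 0, 0, −0.125, −0.25, −0.375. Sxy = 0.25(−0.25) + 0.5(−0.375) = −0.25; slope = −0.40; apparent change = −0.10.

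The literal model gives −0.41, −0.26 and −0.11, so the subject term hardly matters here. With 30% to 60% mortality added, the net error of the literal model ran from −0.40 to +0.18 L/year.

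**Step 3: what the per-subject test keeps.** With 1 to 5 pre-drug FVCs equally likely, 4/5 of subjects have at least two: 8 of 10. Two on-drug FVCs require survival to week 20. At 30% mortality with a constant hazard, 0.70^(20/52) = 0.87, and 8 × 0.87 ≈ 7. At 60%, 0.40^(20/52) = 0.70, and 8 × 0.70 = 5.6; simulation with differing hazards gives about 5.

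**The case against.** Section 8 says mixed effects and cites a mixed-models text. Subject intercepts fitted by least squares contain no random effect, so a random term may well be intended, and a subject slope is one candidate. A reader might infer that the plan has chosen a model without random effects. The text does not support that: the terms are unnamed, not excluded. This stands, and it is why the simulated figures apply to the literal reading only. The missing window remains under any reading.

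A reader might also infer that the test is miscalibrated as it stands, or that it favours pirfenidone. Neither follows. With common slopes and independent errors it holds its level. No FVC variance is given anywhere, and the death effect and the window effect pull in opposite directions. The mortality figure, "Approximately 60% of patients with RCLAD die within one year from respiratory failure", is background on the disease and not a forecast for these subjects.

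The plan states no alpha for FVC, so the rejection rates are measured against an assumed 5% test. That stands too.

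Finally, a SAP is promised and FVC is secondary in an uncontrolled pilot. Both points limit the severity. They do not remove the reason to settle the window early: in an open-label study, a window chosen after on-drug FVC has been seen could decide the result.

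**Conclusion.** The concern holds as a minor point. The one subject term that section 8 names gives a wrong standard error once decline rates differ, and no section defines the pre-drug FVC period. Under the stated assumptions, null rejection for the literal reading runs from well under 5% to about 30%. The estimate can be shifted by up to about 0.27 L/year towards slowing (deaths linked to decline, 60% mortality) or by about 0.1 to 0.4 L/year towards acceleration (window reaching back before onset). The sizes rest on variances and hazards that the documents do not give. What does not rest on them is that the result depends on choices the plan leaves open. No net direction is established.

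**What to change.** In section 8, or in the promised SAP:

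1. Replace the fixed subject effect with a random intercept, random slope and random change in slope at pirfenidone start, tested with small-sample degrees of freedom. If that cannot be fitted, use a one-sample t-test of per-subject slope changes. A random slope with only a common change is not enough: it still rejected 14% to 16% of null trials when slope changes varied (SD 0.4), against 3% to 10% with a random change.
2. Before on-drug FVC is examined, fix the pre-drug window from RCLAD onset, the anchor already used for CT, to first dose. Reconcile this with the synopsis, which describes FVC change only after initiation.
3. Keep the FVC that defined onset in the main analysis and leave it out as a sensitivity analysis. Onset rests on "FVC ≤ 80% of best post-transplant baseline", so that reading tends to be low by selection. Including it gave a false acceleration of 0.09 to 0.25 L/year in simulation, with per-subject rejection of 15% to 34%. But onset also needs FEV1 and CT, and with monthly screening a subject may have few other pre-drug readings, so a blanket exclusion could remove the pre-drug slope altogether. Show both results.
4. Report usable FVCs per subject in each period, and deaths.

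**Cost.** Wording only, but power falls when pre-drug readings are few. With 1 to 5 per subject, the per-subject test has about 15% to 25% power for a slowing of 0.25 L/year, less than the nominal power of the literal model (26% to 44%, part of which is inflated error). The gain is a better-controlled error rate, not power.

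**Limits.** If death follows the on-drug slope, bias remains: +0.13 L/year for the mixed model and +0.06 for the t-test in the strongest setting. If decline slows by itself after onset, a single-arm comparison will credit the drug: one assumed curve gave +0.37 L/year with a window starting at onset.
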